11.1 Inclusion Criteria

1. Hospitalized subjects who are indicated for a screening, diagnostic, surveillance or therapeutic colonoscopy
2. Subjects' age > 22 years
3. Subject has signed the informed consent

11.2 Exclusion Criteria

1. Subjects with known Inflammatory Bowel Disease and / or active Colitis
2. Subjects with active diverticulitis
3. Subjects with known or detected (during colonoscopy) bowel obstruction
4. Subjects with ascites Child Pugh C
5. Subjects who are 30 days post-transplant
6. Subjects under active IV inotropic medications
7. Subjects with LVAD
8. Subjects with known coagulation disorder (INR \geq 2 or platelets <50,000)
9. Subjects with medical and/or hemodynamic instability.
10. Pregnancy (as stated by Subject) or breast feeding

Document Title: Evaluation of the bowel cleansing in hospitalized population using Pure-Vu System	Document No. CL00044	Version 4.0	Page 23 of 44
---	--------------------------------	-----------------------	---------------

11. Subjects with altered mental status/inability to provide informed consent
12. Subjects who have participated in another interventional clinical study in the last 2 months

11.3 Withdrawal Criteria

Subjects may withdraw from the study at their own request or at the request of their legally acceptable representative. The investigator may withdraw a subject from the study at any time for the following reasons:

- ❖ Severe side effects clearly related to the study device.
- ❖ Presence or appearance of exclusion criteria.
- ❖ Appearance of accompanying diseases rendering further participation in the study impossible.
- ❖ A significant protocol violation, as determined either by the sponsor or the investigator
- ❖ Subject noncompliant with investigational procedures

The sponsor must be informed in each withdrawal case. The reason for withdrawal must be recorded in the CRF and in the subject's study file.

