12.0 Study Procedures

12.1 Screening and Informed Consent

A screening/baseline assessment will be performed prior to the scheduled Pure-Vu procedure to ensure subject's eligibility and willingness to participate in the study.

At the screening visit, subjects will be approached to obtain written informed consent prior to any study specific procedures being performed. The purpose of the study and the benefits and risks of the procedures will be explained to the subject and the consent process must be documented accordingly in the medical records. Subjects who agree to study participation must sign an IRB-approved ICF. Subjects will be informed that their participation in this study is voluntary and they may refuse to participate or discontinue from the study at any time. Subjects will be given the opportunity to ask the investigator questions so that they are adequately informed about the research. A copy of the signed informed consent must be provided to the subject and the informed consent process will be documented in source documents.

If new information becomes available that may affect a subject's decision to continue to take part in the study, this information will be discussed with the subject by the investigator.

The following assessments will be performed prior to the scheduled procedure and the results recorded on the appropriate subject CRFs:

- Verification of eligibility criteria and subject risk per guidelines
- Demographics (age, gender, height, weight)
- Surgical and medical history (prior abdominal surgery, GI symptoms)
- General medical history will be assessed based on the subject's clinical condition

Subjects who were found to be ineligible for the study following signature of the Informed Consent Form will be withdrawn from the study and no further follow up will be performed.

Document Title:	Document No.	Version	Page 25 of 44
Evaluation of the bowel cleansing in hospitalized population using Pure-Vu System	CL00044	4.0	

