12.3 Screen Failures

A subject is considered enrolled in the study when the ICF is signed. Only subjects who undergo the colonoscopy procedure with Pure Vu will be followed. Subjects who provide study consent, but then are determined to be ineligible will be considered screening failures and will not require additional study follow-up. The reason for the screening failure will be clearly documented, the Subject "Enrollment and Visit Log" will be completed and the subject eligibility section in visit 1 as well as a "Study Completion" form will be completed in the CRF.

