13.2 Description of statistical methods

Basic demographic and other baseline characteristics will be collected and analyzed for all subjects. Summary statistics (mean, standard deviation, median, minimum and maximum for quantitative variables) will be presented for the total study population. Frequency tables for qualitative data will be provided.

Any deviation from specified statistical plan will be in addition to “per protocol” analysis and will be reported as such. Intent-To-Treat and Post-hoc analysis will be conducted according to the existing data gathered, if necessary.

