13.5 Analysis Populations

Cases withdrawn prior to the Pure-Vu procedure and those with technical failures will be excluded from the primary analysis. Cases with failure to reach the desired colon segment per the intended indication, which cannot be conducted with Pure-Vu, will be excluded from the primary analysis. All subjects who have the Pure-Vu inserted will be included in the safety analysis.

Individual listings of withdrawal / technical failure including descriptive information will be provided.

Document Title:	Document No.	Version	Page 30 of 44
Evaluation of the bowel cleansing in hospitalized population using Pure-Vu System	CL00044	4.0	

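### A subject found ineligible during the colonoscopy loses follow-up under 12.1 and 12.3 as worded, and retention in the primary analysis after a late withdrawal is only implied

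*Combined protocol and SAP*

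**What the plan says.** **Withdrawal.** Section 11.3 states that "The investigator may withdraw a subject from the study at any time for the following reasons". The reasons include "Presence or appearance of exclusion criteria" and "A significant protocol violation, as determined either by the sponsor or the investigator". What makes a violation significant is not defined. The sponsor must be told of each withdrawal, and the reason goes into the CRF.

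**An exclusion that can arise mid-procedure.** Exclusion 3 in 11.2 reads "Subjects with known or detected (during colonoscopy) bowel obstruction".

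**Follow-up of ineligible subjects.** Section 12.1 says that subjects found ineligible after signing consent "will be withdrawn from the study and no further follow up will be performed". Section 12.3 classes subjects who consent and are then determined to be ineligible as screening failures who need no further study follow-up. Neither sentence sets a time limit. The same section 12.3 also says "Only subjects who undergo the colonoscopy procedure with Pure Vu will be followed".

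**Analysis sets.** Section 13.5 removes three groups from the primary analysis: withdrawals before the Pure-Vu procedure, technical failures, and failures to reach the segment that the indication requires. It then says "All subjects who have the Pure-Vu inserted will be included in the safety analysis". Section 13.3 bases the primary assessment on every segment observed. Withdrawal after the procedure is not mentioned in either section.

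**The concern.** Two things are at stake, and the first is the firmer.

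**Safety capture.** A subject whose obstruction is discovered with the device in place has been exposed to the device and may be at higher risk than the average participant. If the ineligibility rule is followed literally, this subject is withdrawn, may be logged as a screening failure, and is not contacted afterwards. The schedule in Appendix A contains only one contact after the procedure day, so losing it means losing all planned later collection of adverse events for that subject.

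**Freedom from bias in the primary result.** The study is open and single-arm. BBPS before and after cleansing is known at the procedure, and 12.5 allows a sponsor representative to attend. A withdrawal decided after that point, on an undefined criterion that the sponsor may determine, is harmless only if the scores already obtained stay in the analysis. The plan points that way but does not say it.

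**Working it through.** The plan gives no sample-size, power or withdrawal-rate figure, so there is no design number to reproduce. The check is mainly a comparison of the text.

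**Step 1: follow one subject through the rules.** Consent is signed, Pure-Vu is inserted, and an obstruction is then detected.

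| Section | What it implies for this subject |
|---|---|
| 11.2, exclusion 3 | Now meets an exclusion criterion |
| 11.3 | May be withdrawn, because an exclusion has appeared |
| 12.1 | Ineligible after consent: withdrawn, no further follow-up |
| 12.3, ineligibility sentence | Screening failure; follow-up not required |
| 12.3, procedure sentence | Underwent the Pure-Vu procedure: belongs to those followed |
| 12.5 | If the cecum was not reached: completes the study as planned |
| 13.5 | Device inserted: in the safety analysis |
| 14.1 | Adverse events collected until follow-up is completed |
| 14.10 | Events monitored until the subject completes the study; longer only if judged device-related |

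The two sentences of 12.3 give different answers, and 12.1 differs from 12.5. Section 13.4.1 describes the safety set differently, as all enrolled subjects, but this subject belongs to it under either description. The subject is therefore counted in the safety denominator while two sections waive the contact that would supply later events. Section 14.10 does not fill the gap, because its extension depends on an event already being known and judged device-related.

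**Step 2: follow a scored subject who is withdrawn afterwards for a violation.** Section 13.5 excludes withdrawals only if they precede the procedure, and 13.3 uses all observed segments. On a plain reading the subject stays in. No sentence states this, and none says that data collected before withdrawal are retained.

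**Step 3: hypothetical subject-level illustration.** This shows what would happen if such subjects were dropped, which the plan does not instruct. The improvement rates and the number removed are assumptions, and every removed subject is assumed to be non-improved.

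The exact 95% interval for x out of n has as its lower limit the 0.025 quantile of Beta(x, n − x + 1), and as its upper limit the 0.975 quantile of Beta(x + 1, n − x).

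As a check of the method, section 6.3 reports 25% [17%, 35%] and 99% [94%, 100%] after 2 of 97 subjects were excluded, which leaves 95. Taking 24/95 gives 25.3% (16.9 to 35.2), and 94/95 gives 98.9% (94.3 to 100.0). Both match after rounding.

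| All kept | Non-improved removed | After removal | Shift |
|---|---|---|---|
| 80/100 = 80.0% (70.8 to 87.3) | 5 | 80/95 = 84.2% (75.3 to 90.9) | 4.2 points |
| 90/100 = 90.0% (82.4 to 95.1) | 5 | 90/95 = 94.7% (88.1 to 98.3) | 4.7 points |
| 95/100 = 95.0% (88.7 to 98.4) | 3 | 95/97 = 97.9% (92.7 to 99.7) | 2.9 points |

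Section 13.3 reports both segments and subjects, and these figures concern subjects only.

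**The case against.** **On follow-up.** The 12.1 sentence stands under screening and consent, directly after a list of assessments made before the procedure, and 12.3 ties screening failure to the visit 1 eligibility form. The authors probably had pre-procedure ineligibility in mind, and 12.5 and 14.1 point towards continued follow-up. This is a fair account of the likely intent. It does not remove the conflict. Neither sentence carries a time limit, exclusion 3 names detection during the colonoscopy, and 12.3 only restricts who is followed before releasing ineligible subjects in its next sentence. Section 12.5 covers failure to reach the cecum, not an exclusion found on the way.

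It can also be said that 13.5 is not contradicted, since it defines who is analysed and not who is contacted. That is correct. The conflict lies within 12.3 and between 12.1 and 12.3; for 13.5 the consequence is incomplete data on a member of the safety set.

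**On the primary analysis.** A reader might infer that no rule keeps late withdrawals in the primary result. The documents do not support that: the time limit in 13.5 and the all-segments basis in 13.3 imply that they stay.

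A reader might also infer that 13.2 removes protocol violators, because it refers to a per-protocol analysis and adds that "Intent-To-Treat and Post-hoc analysis will be conducted according to the existing data gathered, if necessary". The per-protocol sentence, however, concerns departures from the statistical plan, not violations by subjects, and no per-protocol population is defined anywhere. The conditional intent-to-treat wording is loose but does not authorise removing scored subjects.

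Nor does the sponsor withdraw anyone under 11.3. It may determine that a violation is significant, and the withdrawal itself is the investigator's. Withdrawals are also visible, through the CRF and the individual listings promised in 13.5.

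**Conclusion.** The follow-up point holds. As worded, 12.1 and 12.3 allow a device-exposed subject with an exclusion found during colonoscopy to be treated as a screening failure without follow-up. This conflicts with the statement in 12.3 on who is followed and weakens adverse-event capture in the safety set. The number affected cannot be derived, because the documents give no expected frequency of obstruction; it may be small or nil.

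The primary-analysis point holds only as a missing statement. Retention of scored subjects after late withdrawal is implied by 13.3 and 13.5 and should be made explicit, because the withdrawal criterion is undefined and can be applied once the result is known. The shifts of about 3 to 5 percentage points rest on assumed rates, on removal of non-improved subjects only, and on a deletion that the plan does not prescribe. They show why the sentence is worth adding; they do not estimate bias in this study.

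**What to change.** - **12.1 and 12.3:** reconcile the two by limiting screening failure, and the end of follow-up that comes with it, to ineligibility found before Pure-Vu is inserted. Keep the planned follow-up contact for every subject with the device inserted, unless consent is withdrawn.
- **11.3:** refer to that rule, so that withdrawal for an exclusion that appears during the colonoscopy does not cancel the contact.
- **13.5:** state that withdrawal after insertion, for a violation or for an exclusion found during colonoscopy, does not remove observed BBPS scores from the primary analysis. In the listing already promised there, show such withdrawals by reason.

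This leaves the existing technical-failure and failure-to-reach exclusions in 13.5 as they are; whether those are sound is a separate question. The change alters no clinical care. It costs a few sentences and a small extension of a listing. The downside is that the reported improvement rate may be slightly less favourable. If the sponsor already intends the plain reading of 13.3 and 13.5, the primary result does not change.

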11.4 Selection of Investigators and Training

Board-certified gastroenterologists in accordance with US and hospital guidelines will be considered for participation as investigators in this study. Physicians in training (residents, fellows) and physician assistants may assist the Study Investigator in any aspect of the procedure as per standard procedures and practices at his/her institution.

Each Investigator participating in the clinical trial and the associated clinical study staff will receive training on the clinical protocol. This includes training on AE reporting, case report form (CRF) completion, and Good Clinical Practice (GCP), as well as the device and system (including procedural use, device characteristics, shelf life and storage requirements, warnings, and precautions).

Document Title: Evaluation of the bowel cleansing in hospitalized population using Pure-Vu System	Document No. CL00044	Version 4.0	Page 24 of 44
---	--------------------------------	-----------------------	---------------

12.0 Study Procedures

12.1 Screening and Informed Consent

A screening/baseline assessment will be performed prior to the scheduled Pure-Vu procedure to ensure subject's eligibility and willingness to participate in the study.

At the screening visit, subjects will be approached to obtain written informed consent prior to any study specific procedures being performed. The purpose of the study and the benefits and risks of the procedures will be explained to the subject and the consent process must be documented accordingly in the medical records. Subjects who agree to study participation must sign an IRB-approved ICF. Subjects will be informed that their participation in this study is voluntary and they may refuse to participate or discontinue from the study at any time. Subjects will be given the opportunity to ask the investigator questions so that they are adequately informed about the research. A copy of the signed informed consent must be provided to the subject and the informed consent process will be documented in source documents.

If new information becomes available that may affect a subject's decision to continue to take part in the study, this information will be discussed with the subject by the investigator.

The following assessments will be performed prior to the scheduled procedure and the results recorded on the appropriate subject CRFs:

- Verification of eligibility criteria and subject risk per guidelines
- Demographics (age, gender, height, weight)
- Surgical and medical history (prior abdominal surgery, GI symptoms)
- General medical history will be assessed based on the subject's clinical condition

Subjects who were found to be ineligible for the study following signature of the Informed Consent Form will be withdrawn from the study and no further follow up will be performed.

Document Title:	Document No.	Version	Page 25 of 44
Evaluation of the bowel cleansing in hospitalized population using Pure-Vu System	CL00044	4.0	

12.2 Randomization

NA –Single study arm

12.3 Screen Failures

A subject is considered enrolled in the study when the ICF is signed. Only subjects who undergo the colonoscopy procedure with Pure Vu will be followed. Subjects who provide study consent, but then are determined to be ineligible will be considered screening failures and will not require additional study follow-up. The reason for the screening failure will be clearly documented, the Subject "Enrollment and Visit Log" will be completed and the subject eligibility section in visit 1 as well as a "Study Completion" form will be completed in the CRF.

12.4 Colon Preparation

As standard practice in the hospitalized population setting, bowel preparation is prescribed for individuals undergoing a colonoscopy procedure. The typical and recommended bowel prep is the 4 Liters of GoLytly as a split dose. Although this bowel prep is widely prescribed, it is not a requirement that the subject completes the bowel prep prior to the colonoscopy procedure for the study.

12.5 Colonoscopy procedure

Pre-Examination Procedures

- Verify eligibility checked and informed consent was obtained after explaining all risks, benefits, and alternatives to the subject.
- Verify that the study coordinator/nurse has completed the questionnaire regarding the subject's bowel cleansing condition.
- Verify all background/clinical information, demographic and medical history was documented

Document Title: Evaluation of the bowel cleansing in hospitalized population using Pure-Vu System	Document No. CL00044	Version 4.0	Page 26 of 44
---	--------------------------------	-----------------------	---------------

- Verify all connections and assemblies are properly attached (see Instructions for Use)
- Verify device works properly (see Instructions for Use)
- Place and prepare the subject for the colonoscopy procedure.

Colonoscopy Procedures

The insertion during the colonoscopy procedure will be performed by the clinical study investigator(s), experienced in GI endoscopy according to local standard of care. The withdrawal part of the colonoscopy procedure will be performed as per the clinical investigator(s) direction. Physicians in training (residents, fellows) and physician assistants may assist the Study Investigator in any aspect of this part of the procedure as per standard procedures and practices at his/her institution. In cases where upper endoscopy is planned, it will be conducted per the physician's discretion. Anesthesia will be applied as well per the standard of care. In order to ensure correct operation of the Pure-Vu System a Motus GI representative may attend the procedure. Pure-Vu System operation is described in the Instruction for Use.

The colon preparation level for each colorectal segment (ascending, transverse and descending) before the cleansing operation during the insertion phase will be evaluated using the BBPS scoring index (Appendix B).

In case of inadequate bowel preparation defined as BBPS less than 2 in at least one of the colon segments prior Pure-Vu use, the physician will complete a questionnaire as it relates to the subjects management standard of care assuming absence of the Pure-Vu System.

Once the procedure is completed, relevant data will be recorded on the CRF in addition, findings, diagnosis as well as Physician questionnaire will be recorded/completed.

The colonoscopy examination with the Pure-Vu will be recorded on digital media. Only the subject study ID and initials should appear in the recorded video.

The cecum will be documented in a picture, if applicable.

Document Title:	Document No.	Version	Page 27 of 44
Evaluation of the bowel cleansing in hospitalized population using Pure-Vu System	CL00044	4.0	

All optical colonoscopy still pictures will be saved in a digital format. Quality copies of the pictures taken during optical colonoscopy will be provided to the sponsor and the optical colonoscopy report will be reviewed as part of the monitoring process.

These videos and pictures will be archived and may be used in future analyses to, for example, provide further information about observed lesions or to assess study quality.

Specific situations occurring during colonoscopy

- If the attempt to reach the cecum is failed, the investigator shall perform the procedure with a pediatric or any other colonoscope he/she may choose without Pure-Vu. The subject will complete the study as planned.
- If a medical condition requiring treatment is detected during colonoscopy, the subject will be treated as per the standard care.

Post-Examination Follow-up

Subjects will be transferred to recovery room for observation per clinical site's colonoscopy protocol and will continue his/her medical flow as per the standard of care. Follow-up will be conducted 2 business days (+/- 48 hours) after the procedure to verify that there has been no change in their well-being. Any AE will be documented in the CRF.

Before a subject is considered "lost to follow-up", there must be at least two documented attempts to contact the subject.

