9.0 Study Endpoints

9.1 Primary endpoints

The rate of improved cleansing level per segment will be evaluated by the BBPS (1) scoring index pre- and post- Pure-Vu use during a colonoscopy examination.

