13.3 Primary Endpoint Analysis

The primary endpoint is improving the bowel cleansing level, as determined by BBPS scoring index, assessed per segment (cecum and ascending / transverse / descending, sigmoid and rectum).

The primary statistical hypothesis is that the cleansing level post Pure-Vu procedure will be significantly improved as compared to the cleansing level pre procedure (prior the Pure-Vu use). The primary performance assessment will be based on data from all colon segments observed during the colonoscopy procedure.

The count and percentage of segments and subjects with improved BBPS after the Pure-Vu cleansing procedure will be presented together with 95% confidence intervals.

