13.4.2 Efficacy Analysis

Cecal Intubation Rate

The count and percentage of subjects for which cecum could be reached by the colonoscope with the Pure-Vu will be presented together with 95% confidence intervals.

Proportion of subjects with successful colonoscopy at first attempt

Successful colonoscopy at first attempt is defined as complete procedure conducted as scheduled for the intended indication.

Frequency counts, percentages, and 95% confidence intervals will be provided. In addition, the above proportion will be compared vs. the proportion of subjects that would have underwent a complete procedure at first attempt assuming absence of the Pure-Vu System (as per the data to be captured by the Patient Management Direction). Chi-square or Fisher's exact test, as appropriate, will be performed to evaluate the difference between the two clinical set-ups.

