20.0 Appendixes A: Study Design and Schedule of Assessment

	Visit 1	Follow Up
Days	0	2 Business Days (± 48 hours)
Informed Consent	X	
Eligibility assessment (medical records, BMI, etc.)	X	
Medical History, Concomitant Medications, and Demographic details	X	
Assessment of patient's bowel preparation questionnaire	X	
*Assessment of patient's management Directions (filled-in by the physician)	X	
Colonoscopy Procedure	X	
Follow Up	X	X
Adverse Events Reporting	X	X

*for subjects with inadequate bowel cleansing level in at least one segment at baseline.

Document Title:	Document No.	Version	Page 44 of 44
Evaluation of the bowel cleansing in hospitalized population using Pure-Vu System			

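### The plan does not require the no-device management form, the stated source of the 13.4.2 comparator, to be answered before the operator sees the Pure-Vu result, nor baseline BBPS to be written down before cleansing

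*Combined protocol and SAP*

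**What the plan says.** **Baseline score.** Section 12.5 says the preparation level of each segment "before the cleansing operation during the insertion phase will be evaluated using the BBPS scoring index". That fixes when the score is formed. It does not say when the score is written down.

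**Recording.** For data arising in the procedure, section 12.5 gives one instruction on timing: "Once the procedure is completed, relevant data will be recorded on the CRF in addition, findings, diagnosis as well as Physician questionnaire" are to be recorded or completed.

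**No-device form.** The trigger in section 12.5 is "In case of inadequate bowel preparation defined as BBPS less than 2 in at least one of the colon segments prior Pure-Vu use". When it is met, "the physician will complete a questionnaire as it relates to the subjects management standard of care assuming absence of the Pure-Vu System". Sections 3.0 and 10.0 say the same in similar terms. Appendix A lists "Assessment of patient's management Directions (filled-in by the physician") under Visit 1, the day of the colonoscopy, with no order within the visit.

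**Use.** The primary endpoint in 9.1 rests on the BBPS "scoring index pre- and post- Pure-Vu use during a colonoscopy examination", analysed in 13.3 as the proportion of segments and subjects improved, with 95% confidence intervals. In 13.4.2 the observed first-attempt success proportion is "compared vs. the proportion of subjects that would have underwent a complete procedure at first attempt assuming absence of the Pure-Vu System", taken from the Patient Management Direction data and tested by chi-square or Fisher's exact test.

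**The concern.** The study has one arm, and the documents name no blinded or independent BBPS reader. The procedure video is archived, with later use optional. The order of events is therefore the main protection available against an outcome-aware answer, and the plan does not secure it.

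The no-device form matters most. Its answers are the only stated source of the comparator in 13.4.2, and that comparison carries a p-value. An operator who has watched a poorly prepared bowel come clean, or fail to, is asked what would have happened otherwise. If the form is answered at that point, knowledge of the result can enter the answer, and an answer free of it cannot be recovered later.

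The baseline score is half of the primary endpoint. If it is first written down after the procedure, it too can drift, though it was formed beforehand.

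**Working it through.** The plan derives no figure on this point, so there is nothing to reproduce. The check is a reading of the text, followed by a sensitivity illustration.

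**Step 1: what is timed and what is not.**

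| Item | When formed or triggered | When written down |
|---|---|---|
| Nurse or coordinator preparation questionnaire | Before the colonoscopy (10.0) | Before; verified at the pre-examination step (12.5) |
| Baseline BBPS | During insertion, before cleansing (12.5) | Not stated separately; procedure data go on the CRF afterwards |
| No-device management form | Triggered by a pre-use score below 2 | Not stated |
| Physician questionnaire | Not stated | After the procedure (12.5) |

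The first row shows that the protocol times a form when it wants it early. In the trigger wording, the reference to the period before Pure-Vu use qualifies the score, not the completion of the form. List order does not help: sections 3.0 and 10.0 put the form after the colonoscopy item, section 12.5 puts it before the post-procedure sentence, and Appendix A puts it above the colonoscopy row.

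**Step 2: two readings.** If the physician questionnaire is the no-device form, completion after the procedure is explicit. If it is a different form, the no-device form has no stated time. Neither reading requires an answer before the result is seen.

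**Step 3: sensitivity of 13.4.2.** Assumptions: N = 100 (the maximum), two-sided 0.05 (the plan states no alpha), and the same true first-attempt success with and without the device, A of 100. This null is chosen to gauge sensitivity and is not a forecast. Let k answers change from would complete to would not complete, so that A/100 is compared with (A − k)/100.

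For A = 95 and k = 8: pooled proportion (95 + 87)/200 = 0.91; SE = √(0.91 × 0.09 × 2/100) = 0.0405; z = 0.08/0.0405 = 1.98; p = 0.048.

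| A | Smallest k, chi-square (uncorrected) | Smallest k, Fisher |
|---|---|---|
| 90 | 10 (p = 0.048) | 11 (p = 0.049) |
| 95 | 8 (p = 0.048) | 10 (p = 0.032) |
| 98 | 7 (p = 0.030) | 8 (p = 0.033) |

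**Step 4: shift in the comparator rate.** Shift = share inadequately prepared × change in their answers. Assumed share 40% to 75%: the upper value is 100% − 25% from the earlier study in section 6.3, which reduced the preparation on purpose; the lower value has no source in the documents. Assumed change 10 to 30 percentage points. Result: 0.40 × 0.10 = 4 points, to 0.75 × 0.30 = 22.5 points. The same arithmetic applies in either direction.

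**Step 5: primary endpoint.** If a share h of truly unimproved segments had the baseline noted too low, the reported rate is p + h(1 − p). With h from 5% to 30% (assumed):
- true 50% reads 52.5% to 65%;
- true 70% reads 71.5% to 79%;
- true 90% reads 90.5% to 93%.

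This applies only if late recording actually alters a score already formed.

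**The case against.** **The baseline is assessed prospectively.** A reader might infer that baseline BBPS is recalled after the procedure. The documents do not say so. The score is formed during insertion; the post-procedure sentence concerns CRF entry, and section 16.0 provides for source verification. This stands, and it makes the primary-endpoint risk the smaller one. It does not close the gap, because no source record of the score is required before cleansing.

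**The physician questionnaire may be another form.** It is listed with findings and diagnosis and carries no condition, whereas the no-device form is conditional and goes by another name in 13.4.2 and Appendix A. A reader might infer that the protocol instructs late completion of the no-device form. That is not established; what is established is that early completion is not required.

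**The direction is not shown.** Knowing that the examination was completed could lead an operator to judge that it would have been completed anyway, which works against the device. This stands.

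**It is a pilot, and the comparator is subjective whenever it is answered.** True, and an early answer still comes from an operator who knows the device is mounted. But 13.3 states a hypothesis of significant improvement, 13.4.2 adds a test, and 15.7 foresees regulatory and marketing use. Knowledge of the outcome is a separate source of bias, and it can be removed at little cost.

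**Conclusion.** The concern holds as a gap in data capture. Followed as written, the plan allows the unblinded operator to give the answers behind the 13.4.2 comparison after seeing the Pure-Vu result. For the primary endpoint the gap is narrower: only the recording of the score may be late, not its assessment.

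The effect plausibly favours the device, but the documents determine neither its direction nor its size. The figures of 7 to 11 changed answers, 4 to 22.5 points, and the shifts in the improved rate rest on assumed inputs. They show that a modest number of outcome-aware answers could matter, not that this will happen. A firm claim that hindsight inflates the results would go beyond the text.

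The change should be made before enrolment, or for the subjects still to be enrolled, since late answers cannot be repaired in analysis.

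**What to change.** Amend section 12.5 and the CRF or source worksheet:

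1. The investigator calls out each segment's pre-cleansing BBPS, and staff already present note it on a source worksheet before the cleansing function is used in that segment. The documents mention the nurse or coordinator only for the form completed before the procedure, so the amendment should leave open who acts as scribe.
2. Once a pre-cleansing score below 2 triggers it, the Patient Management Direction form is answered, with fixed options, before the cleansing result is seen. The time and the segments seen so far are noted, and the answer is not edited later. State whether this form and the physician questionnaire are the same.
3. In 13.4.2, forms completed after cleansing are flagged, and the comparison is repeated without them as a sensitivity analysis.

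The time should be written on the form itself: the plan describes the video as a recording of the examination and says nothing about it showing when a form was answered.

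The cost is a short wording change, a worksheet, and a short pause during the procedure. The main drawback is that an early answer may rest on only the segments seen so far, which is why those are noted. The change removes knowledge of the outcome, not the operator's general lack of blinding.
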